5.1 EFFICACY/EFFECTIVENESS OBJECTIVES

Efficacy is assessed by describing the complete responses in daily clinical practice in Spain in patients with metastatic renal carcinoma treated with first-line Sunitinib, defined as the documented disappearance of all lesions in the investigator's opinion in at least 2 consecutive CT scans. The treatment may be with Sunitinib alone (CR Suni) or Sunitinib plus a local treatment to eliminate residual disease (CR + local treatment).

The baseline characteristics of both patient and tumour will be described to seek predictive response factors. The following variables will be considered:

- Demographic characteristics (age at the start of treatment)
- Comorbidities: cardiac, renal, endocrine, autoimmune and hepatic.
- Previous nephrectomy
- Classification of the risk group according to Motzer and/or Heng criteria and of the association between each one of the prognostic variables, such as: patient baseline status, time elapsed from nephrectomy to the start of systemic treatment, presence of anaemia, corrected calcium, LDH levels, neutrophil and platelet levels.
- Tumour data: histology, Fuhrman grade, presence of tumour necrosis and number and location of metastases (organs involved).

Secondary efficacy objectives evaluated will be time on treatment with Sunitinib until CR, duration of complete response and the time elapsed from CR to disease stabilisation/progression or change of treatment due to unacceptable toxicity or death from any cause.

The subjects with the greatest clinical benefit will be evaluated on the basis of the therapeutic strategy adopted in order to develop recommendations to be followed in patients who obtain CR. Moreover, the decision to discontinue treatment after a period of maintenance of CR and the pharmacological group by the mechanism of action used in second line after disease the progression will be evaluated.

5.2 SAFETY OBJECTIVES

The safety of Sunitinib will be evaluated by describing the incidence of the serious and non-serious adverse events of highest grade explicitly attributed to Sunitinib in the patient's medical history, as well as the grade of the associated adverse event if it or they lead to treatment discontinuation at some point due to toxicity.

5.3 OTHER OBJECTIVES

The evolution of the neutrophil/leukocyte ratio throughout treatment will be analysed: at 4-6 weeks, 3 months, 6 months, 9 months, 12 months and then every 6 months in the available laboratory data close to these dates.

Several studies suggest that a high neutrophil/leukocyte ratio (NLR) is associated with a poorer disease prognosis. The analysis of the evolution of these two haematological parameters for subsequent exploratory analyses is established as an additional objective.

5.4 COVARIATES

All the covariates have been collected on the paper CRF designed for this study as specified in the study protocol.

Variable	Role	Operational definition
ECOG	Epidemiological datum (covariate)	Risk groups
Patient age at time of diagnosis	Epidemiological datum (covariate)	Age
TNM tumour stage (T describes the size of the tumour and the spread of the cancer to nearby tissue; N (nodes) describes the spread of cancer to nearby lymph nodes and M stands for metastases)	Epidemiological datum (covariate)	Tumour staging
Tumour histology	Epidemiological datum (covariate)	Pathological Anatomy
Fuhrman tumour grade	Epidemiological datum (covariate)	Pathological Anatomy
KPS	Epidemiological datum (covariate)	Risk groups
Previous nephrectomy	Epidemiological datum (covariate)	Surgery
Cardiac, renal, endocrine, autoimmune and hepatic comorbidities.	Epidemiological datum (covariate)	Disease data
Classification of the prognostic risk group	Epidemiological datum (covariate)	Risk groups
Patient baseline status	Epidemiological datum (covariate)	Risk groups
Time elapsed from the nephrectomy to the start of systemic treatment	Epidemiological datum (covariate)	Risk groups
Haemoglobin	Epidemiological datum (covariate)	Risk groups
Corrected calcium	Epidemiological datum (covariate)	Risk groups
LDH levels	Epidemiological datum (covariate)	Risk groups
Lymphocytes	Epidemiological datum (covariate)	Risk groups
Platelets	Epidemiological datum (covariate)	Risk groups
Baseline Neutrophil/Lymphocyte rate and at 6 weeks of treatment, 3 months, 6 months, 9 months, 12 months and then every 6 months.	Epidemiological datum (covariate)	Risk groups

PFIZER CONFIDENTIAL

Variable	Role	Operational definition
Number of metastases	Disease data (covariate)	Disease data
Number of organs with metastases	Disease data (covariate)	Disease data
Time on treatment before reaching CR	Secondary objective	Disease data
Duration of CR	Secondary objective	Disease data
Reason why CR ends: progression, tumour stabilisation or intolerable toxicity	Disease data (covariate)	Disease data
Dosage and regimens of Sunitinib	Treatment data (covariate)/Secondary objective	Treatment data
Temporary treatment interruptions	Treatment data (covariate)	Treatment data
Definitive interruption of treatment after reaching CR	Treatment data (covariate)	Treatment data
Active patient participation in the decision to interrupt the treatment definitively once CR is obtained	Patient empowerment (covariate)/Secondary objective	
Time on treatment with Sunitinib once CR is reached	Treatment data (covariate)	Treatment data
Local treatment techniques of residual lesions	Secondary objective	Treatment data
PA (pathological anatomy) of the metastasectomy: histology and degree of necrosis	Disease data (covariate)	Disease data
Highest grade of adverse events related to the treatment with Sunitinib	Secondary objective	Treatment data
Serious adverse events (SAEs) during treatment with Sunitinib	Secondary objective	Treatment data
Pharmacological group of second-line treatment after disease progression after a period of time in CR (TKI, mTOR, Immunotherapy)	Secondary objective	Treatment data
Causes of death	Disease data (covariate)	Disease data

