1. LIST OF ABBREVIATIONS

Abbreviation	Definition
AE	Adverse Event
AEM	Adverse event monitoring
AEMPS	Agencia Española de Medicamentos y Productos Sanitarios (Spanish Agency of Medicines and Medical Devices)
AR	Autonomous Regions
AUC	Area under the curve
	Heng risk criteria for anti-VEGF targeted therapies; Prognostic Factors for poor Overall Survival: KPS <80 Time from diagnosis to start of treatment <1 year Anaemia Hypercalcaemia Neutrophilia Thrombocytosis 0 Factors: favourable prognosis group 1-2 Factors: intermediate prognostic group ≥3 Factors: poor prognostic group.
Classification of the prognostic group according to Heng	
Continuous CR	Continuous CR with no changes in the last recorded imaging test

	(CT).
CR	Complete Response
CR + Local treatment	Complete pharmacological response and with local treatment
CR investigator	Complete response: disappearance of all measurable lesions according to investigator's criteria in at least 2 consecutive CT scans
CRF	Case Report Form
CT scan	Computerised axial tomography
CTCAE version 4	Common Terminology Criteria (Common Terminology Criteria for Adverse Events, version 4) of the U.S. Department of Health and Human Services
CVA	Cardiovascular Accident (Stroke)
DMP	Data management plan
DOR	Duration of Response
DOR Duration of Complete Response (CR)	Duration of complete response (CR) to sunitinib; date from the first Computerised axial tomography (CT) scan in which CR was detected to the CT scan in which there was disease progression. If CR continues, continuous CR must be indicated.
DP	Disease Progression
ECOG	Eastern Cooperative Oncology Group. Scale to measure the quality of life of oncology patients with scores running from 0 to 5
eCRF	Electronic Case Report Form
EDP	Exposure during pregnancy
FDA	Food & Drug Administration
GCP	Good Clinical Practice

HFS	Hand-Foot Syndrome
IC	Informed Consent
ICH	International Conference on Harmonisation
IEC	Independent Ethics Committee
KPS	Karnofsky Performance Scale. Scale to quantify the general well-being of patients with cancer and activities of daily living
LDH	Lactate Dehydrogenase
mRCC	Metastatic Renal Cell Carcinoma
mTOR	Mammalian Target of Rapamycin
N/L Ratio	Neutrophil/lymphocyte ratio
NIS	Non-interventional study
ORR	Objective Response Rate
OS	Overall Survival
PFS	Progression-Free Survival
PR	Partial Response

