7. HYPOTHESIS AND OBJECTIVES

This study is a retrospective registry of cases of CR to treatment with sunitinib in patients with metastatic renal cell carcinoma and has a purely descriptive purpose. Therefore, no previous hypothesis has been established.

7.1. Primary objectives:

To describe complete responses in daily clinical practice in Spain between 2007 and 30 October 2018, such as the documented disappearance of all lesions in the investigator's opinion on at least 2 consecutive CT scans.

To look for associations between CR from a macroscopic point of view and the baseline characteristics of both the patient and the tumour, such as:

- Demographic characteristics (age at the start of treatment)
- Comorbidities: cardiac, renal, endocrine, autoimmune and liver.
- Previous nephrectomy

- Classification of the risk group according to Motzer and/or Heng criteria and the association between each prognostic variable, such as: baseline patient status, time from nephrectomy to systemic treatment start, presence of anaemia, corrected calcium, LDH levels, neutrophil levels and platelet levels.
- Tumour data: histology, Fuhrman grade, presence of tumour necrosis and number and location of metastases (organs involved).

7.2. Secondary objectives:

- **To establish recommendations** to be followed **in patients who obtain CR to sunitinib treatment** based on the case recording and the adopted therapeutic strategy that obtained the greatest clinical benefit.
- To define **the median time on treatment with sunitinib until lesion complete remission is reached in the patient responsible physician opinion.**
- To define **the median duration of CR.**
- The time elapsed from the confirmation of CR to disease stabilisation/progression or change of treatment due to unacceptable toxicity or death from any cause will be collected.
- **The dose and treatment regimens used will be recorded.** In the case of changes in the treatment dose (increase or reduction), the reason (toxicity, efficacy, decision taken after lesion elimination or upon request of the patient) will be specified.
- **Description of local treatment techniques** if they were used and at what time they were applied. In the case of a pathology report on the resected part, the percentage of necrosis and histology will be recorded, as well as the surgical complications in the case that they arose.

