5 OBJECTIVES AND VARIABLES

The primary objective of the study is *to identify patients with metastatic renal cell carcinoma (mRCC) who obtained a complete response (CR) to treatment with Sunitinib exclusively or with Sunitinib and a local treatment to eliminate residual disease in the opinion of the clinician. Complete response (CR) is defined as the disappearance of all measurable lesions according to the investigator's criterion in at least 2 consecutive CT scans.*

The clinical baseline characteristics of these patients and the tumour will be described in order to look for predictive response factors.

[figure not shown]
The intention is to describe the therapeutic strategy used in patients who obtained the greatest clinical benefit in the cases described once the macroscopic lesions were eradicated in order to draft recommendations to be followed once the registry's statistical analysis is available.

The variables to be analysed for this study will be obtained from the patients' medical records and case report forms according to the protocol. The data will be recorded on the paper CRF designed for this study where the following patient information will be included:

DEMOGRAPHIC AND DISEASE INFORMATION

- 1) Age at the start of treatment for metastatic disease
- 2) Functional status, measured by the ECOG scale (0, 1, 2, 3, 4) and/or by means of the KPS (Karnofsky Performance Status) scale, at the start of treatment (see annex I)
- 3) Motzer and Heng prognostic criteria
- 4) Laboratory data (haemoglobin, leukocytes, corrected calcium, LDH levels, lymphocytes, platelets, neutrophils, lymphocytes)
- 5) Comorbidities
- 6) Date the disease was diagnosed
- 7) Metastasis site(s) and number
- 8) Furhrman grade (I, II, III, IV)

PFIZER CONFIDENTIAL

- 9) Tumour stage (TNM)
- 10) Previous nephrectomy
- 11) Necrosis

TREATMENT

- 1) Start date of treatment with first-line Sunitinib
- 2) Initial dose and treatment regimen
- 3) Type of treatment received (monotherapy or in combination with local treatment) and technique used in the case of local treatment
- 4) Response to treatment.
- 5) Date of completion of the treatment after CR if treatment is interrupted
- 6) Modification of dosage and/or treatment regimen, number of changes in the dose, reason, date and new dose
- 7) Dose interruptions, number of interruptions, reason, date of interruption and restart and new dose

CCI

- 9) Adverse reactions

POST-TREATMENT

- 1) Continuation of treatment in 1st line

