- 2) End date and reason
- 3) Date of progression
- 4) Date of and reason for death
- 5) Post-Sunitinib treatments (another TKI, mTOR, immunotherapy)

The following aspects will be assessed using the variables collected:

- **Time from nephrectomy to the start of systemic treatment:** defined as the time interval from the day of the nephrectomy to the day treatment with Sunitinib started.
- **Time to CR:** defined as the time interval from the day treatment with Sunitinib started until the day the complete response is documented in the first CT scan without lesions.
- **Duration of treatment with Sunitinib once CR is reached:** defined as the time interval from the day on which the complete response is documented until the day that the definitive discontinuation of the treatment is confirmed, either at the patient's own decision or at the doctor's decision.
- **Time to progression (TTP):** defined as the time interval from the day on which the complete response is documented until the first day that objective tumour progression, if any, is observed.
- **Time to change of treatment:** in patients who continue treatment with Sunitinib once the lesions have disappeared, it is defined as the time interval from the day on which the complete response is documented until the first day on which the change of treatment due to unacceptable toxicity is documented, as applicable.
- **Time to death:** defined as the time interval from the day on which the

Pfizer Confidential

complete response is documented to the day on which death from any cause is documented, if it occurs.

- **Duration of complete response (DOR):** defined as the time interval from the date on which the complete response to Sunitinib is identified until the date of the CT scan conforming tumour progression, the change of treatment due to unacceptable toxicity, death from any cause or until the date of the last follow-up at the close of the study. It represents the time that the patient survives without signs of disease.

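### The Motzer and Heng time factor runs from diagnosis, but the plan derives only the interval from nephrectomy, so the scores' own factor is not examined individually

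*SAP*

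**What the plan says.** **Score definitions.** Protocol section 1 lists the Heng factors as "Prognostic Factors for poor Overall Survival: KPS <80 Time from diagnosis to start of treatment <1 year Anaemia Hypercalcaemia Neutrophilia Thrombocytosis". The Motzer (MSKCC) entry has the same time factor, "Time from diagnosis to start of treatment <1 year".

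**Objectives.** The bullet on the Motzer/Heng classification and its individual prognostic variables gives a different time item. Protocol 7.1 has "time from nephrectomy to systemic treatment start, presence of anaemia, corrected calcium, LDH levels, neutrophil levels and platelet levels", and SAP 5.1 has "time elapsed from nephrectomy to the start of systemic treatment, presence of anaemia, corrected calcium, LDH levels, neutrophil and platelet levels". The protocol abstract and SAP 2.2 agree with these.

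**Derivation and covariates.** SAP 5 has the nephrectomy interval "defined as the time interval from the day of the nephrectomy to the day treatment with Sunitinib started". SAP 5.4 lists "Time elapsed from the nephrectomy to the start of systemic treatment" and assigns it to the risk-group variables. SAP 5 also collects "Date the disease was diagnosed" and, as a separate item, "Motzer and Heng prognostic criteria".

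**Analysis.** SAP 7.2.2 summarises the nephrectomy interval as a continuous variable and tabulates previous nephrectomy as yes or no. SAP 7.2.4 describes the interval in the same bullet as previous nephrectomy. Its log-rank list names neither time variable. Its Cox paragraph calls for a multivariable model of all prognostic factors without listing them. SAP 6 replaces no missing values except incomplete dates.

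**The concern.** The primary objective promises to look at the variables that make up the two risk scores one by one. For the time component, the variable named in the objectives is not the one in the protocol's own score definition, and the one in the definition is never constructed. A reader of the final report could take a result for time from nephrectomy as a result for the scores' time factor. The two intervals coincide only when nephrectomy and diagnosis fall on the same date.

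A second problem follows from the choice of origin. Nephrectomy is not an inclusion criterion, so some eligible patients have no nephrectomy date and no interval. Put into a multivariable model for all patients, the variable removes them. Previous nephrectomy, itself a named baseline characteristic, then has no contrast left in that model.

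**Working it through.** The plan states no figure on this point, so there is none to reproduce. The check compares the sections and then sizes the affected group.

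**1. Score factors against the variables analysed**

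| Factor in protocol section 1 | Objective bullet (protocol 7.1, SAP 5.1) | Log-rank list (SAP 7.2.4) |
|---|---|---|
| KPS <80 | baseline status | baseline status, with ECOG |
| Diagnosis to treatment <1 year | replaced by nephrectomy to treatment | not named |
| Anaemia | named | named |
| Hypercalcaemia | corrected calcium | corrected calcium |
| LDH (Motzer) | named | named |
| Neutrophilia, thrombocytosis (Heng) | named | named |

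Time from diagnosis is the only score factor with no counterpart in either list.

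**2. Relation between the two intervals**

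Time from diagnosis = time from nephrectomy + (nephrectomy date − diagnosis date).

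If nephrectomy never precedes diagnosis (an assumption), the bracket is zero or positive, so the nephrectomy interval is equal to or shorter than the score's interval. The documents give no distribution for the gap, so the number of patients for whom it matters cannot be computed.

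**3. Patients with no nephrectomy interval**

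Inputs:
- N of about 90 (SAP 4.1).
- 0% without nephrectomy in the French complete-response series, where all 64 patients had been nephrectomised (protocol section 6).
- 4% without nephrectomy in the Czech registry cohort, where 96% had been nephrectomised (protocol section 6).

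Expected number = N × share, with a binomial 95% range:
- 0%: 90 × 0 = 0.
- 4%: 90 × 0.04 = 3.6, range 0 to 8; P(at least one) = 1 − 0.96^90 = 0.97.

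For sensitivity, with shares that are assumptions and not taken from the documents:
- 10%: 90 × 0.10 = 9, range 4 to 15.
- 15%: 90 × 0.15 = 13.5, range 7 to 20.

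**4. Consequence if the interval enters the Cox model**

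The date rules in SAP 6 complete a partly known date. They cannot supply a date for an operation that did not take place. A complete-case fit therefore keeps only nephrectomised patients. Previous nephrectomy equals yes for everyone left, and its hazard ratio cannot be estimated. This holds however few patients are lost.

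**The case against.** The strongest reply is that the nephrectomy interval is a surgical covariate in its own right and was never meant to stand in for the score factor. SAP 7.2.4 places it with previous nephrectomy and puts the Motzer/Heng classification in a separate bullet. The rationale cites a Spanish study in which time from nephrectomy to metastasis was related to PFS, which is a different interval but shows interest in nephrectomy timing. The risk-group label in SAP 5.4 is weak evidence, because lymphocytes and the neutrophil/lymphocyte ratio carry it too and neither is a factor in the score definitions. The objective's list is also illustrative, in a study without hypotheses. All of this stands, and it is a reason to keep the variable. It does not fill the gap: on this reading too, the scores' time factor is not analysed individually.

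Three stronger readings are tempting, and the documents support none of them.

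- A reader might infer that the Motzer and Heng groups are calculated with the wrong date. The classification is its own collected item, its factors are defined with time from diagnosis, and no section computes it from the nephrectomy date.
- A reader might infer that patients are misclassified across the one-year cut. The plan applies no cut to the nephrectomy interval.
- A reader might infer that about four patients will be lost. That needs the interval to enter the Cox model, which SAP 7.2.4 does not state, and it uses the Czech share while ignoring the French series, which gives none.

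**Conclusion.** The point holds in a limited form and is minor. The score definitions and the objectives disagree on the origin of the time factor. The SAP resolves this by deriving only the nephrectomy interval, so the factor that belongs to both scores is left out of the individual-variable analyses although its date is collected. This rests on comparing the sections and on no numerical assumption. It concerns the individual component and not the risk groups.

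The loss of patients is conditional. If the nephrectomy interval enters the Cox model, about 0 to 8 of 90 patients drop out, assuming a share without nephrectomy between those of the two cited cohorts. In that model the nephrectomy effect is not estimable.

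**What to change.** In SAP 5, 5.4, 7.2.2 and 7.2.4:

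- Derive time from diagnosis to start of sunitinib, grouped as <1 versus ≥1 year, from the collected diagnosis date, and state which diagnosis that date refers to.
- Use this variable as the individual Motzer/Heng time component in the log-rank and Cox analyses.
- Keep time from nephrectomy as a separate variable, described and analysed in nephrectomised patients only, and leave it out of the all-patient Cox model.
- State whether the risk group is recorded by the investigator or derived from its factors, and align the objective bullet with the score definitions.

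The cost is one derived variable and SAP wording, with no new data collection.

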8.2.2. Exclusion Criteria

Patients who meet any of the following criteria will not be included in the study:

PFIZER CONFIDENTIAL

1. Patients treated with another drug other than Sunitinib.
2. Patients with no radiology reports proving CR.
3. Patients with no record of the dose and regimen received with Sunitinib.
4. Patients who achieved complete remission after 30 October 2018.

Variables

ECOG	Eastern Cooperative Oncology Group	Risk groups
Age of the patient at the time of diagnosis	Epidemiological data	Years
TNM stage (T describes the size of the tumor and the spread of the cancer to nearby tissue; N describes the spread of the cancer to the nearby lymph nodes and the letter M describes the metastases)	Epidemiological data	Tumor stage
Histology of the tumor	Epidemiological data	Pathological anatomy
Tumor Fuhrman grade	Epidemiological data	Pathological anatomy
KPS	Karnofsky Performance Status	Risk groups
Previous nephrectomy	Epidemiological data	Surgery
Cardiac, renal, endocrine, autoimmune and hepatic comorbidities.	Epidemiological data	Disease data
Risk group classification	Epidemiological data	Risk groups
Baseline status of the patient	Epidemiological data	Risk groups
Time from nephrectomy to the start of systemic treatment	Epidemiological data	Risk groups
Hemoglobin	Epidemiological data	Risk groups
Calcium correction	Epidemiological data	Risk groups
LDH levels	Epidemiological data	Risk groups
Lymphocytes	Epidemiological data	Risk groups
Platelets	Epidemiological data	Risk groups

PFIZER CONFIDENTIAL

Neutrophil/lymphocyte index at baseline and after 6 weeks of treatment, at 3 months, at 6 months, at 9 months, at 12 months and then every 6 months	Epidemiological data	Risk groups
Number of metastases	Disease data	Disease data
Number of organs with metastasis	Disease data	Disease data
Median time with treatment before reaching the CR	Treatment data	Disease data
Median duration of the CR	Treatment/disease data	Disease data
Reason why CR ends: progression, tumor stabilization or intolerable toxicity	Disease data	Disease data
Doses and schemes of Sunitinib	Treatment data	Treatment data
Temporary treatment interruptions	Treatment data	Treatment data
Definitive treatment interruption after reaching CR	Treatment data	Treatment data
Active participation of the patient in the decision to definitively interrupt the treatment once the CR has been reached	Patient empowerment	

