- Time on treatment with Sunitinib until complete remission of lesions, calculated as the difference between treatment start date and CR confirmation date (2nd CT scan).
- Duration of complete remission (DOR)
- Progression-free survival (PFS) or time from remission to disease progression, change of treatment due to unacceptable toxicity or death. It will be calculated as the time elapsed from the RC confirmation date (2nd CT scan) until the date of progression/death or change of treatment for unacceptable toxicity, as applicable, or else it will be censored on the date of the last patient follow-up.

Taking into account the asymmetry normally observed in the distribution of survival times and that follow-up periods may be uneven (different study entry date), the Kaplan-Meier method will be used to estimate the median time to CR together with its 95% confidence interval. The median will indicate when complete remission of the disease occurred in 50% of patients.

In order to find associations between time to CR and the baseline features of both patient and tumour, a log-rank test will be used for comparison between groups and the determination of the statistical significance of the correlation between each of the baseline variables and the time to complete remission of disease. The following baseline characteristics are considered:

[figure not shown]
- Demographic characteristics
- Comorbidities
- Tumour data
- Prior nephrectomy in the treatment of metastatic renal cancer
- Classification of the risk group according to Motzer and/or Heng criteria.
- Patient's baseline status, including ECOG grade, presence of anaemia, corrected calcium, LDH levels, neutrophil and platelet levels.

This analysis will establish which baseline characteristics are associated with a shorter complete response time to treatment.

As part of the secondary objectives, the doses and treatment regimens observed in the sample will also be descriptively summarised by means of absolute and relative frequencies. In the case of changes in the treatment dose, the frequency of patients with dose increase, dose reduction and changes in the rest regimen will be specified. Similarly, the most frequent reasons for changes in dosage and/or treatment regimen to RC will be reported.

Frequencies of the type of treatment received will be presented, depending on whether it

Pfizer Confidential

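### Tumour stabilisation is named as an end of complete response in the objective and the recorded reason, but it is not an event in DOR, TTP or PFS and is never defined

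*SAP*

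**What the plan says.** Four places bear on this point.

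- **Recorded variable.** The protocol's variables table (printed after the exclusion criteria in 8.2.2; 8.3 in the table of contents) has "Reason why CR ends: progression, tumor stabilization or intolerable toxicity". SAP 5.4 repeats it: "Reason why CR ends: progression, tumour stabilisation or intolerable toxicity". The protocol leaves full definitions to the SAP, but the operational definition given there for this row is only a generic label, disease data.
- **Secondary objective.** SAP 5.1 sets out to evaluate "the time elapsed from CR to disease stabilisation/progression or change of treatment due to unacceptable toxicity or death from any cause". Protocol 3 and 7.2 and SAP 2.2 have equivalent wording.
- **Analysed events.** In SAP 5, duration of complete response (DOR) runs "until the date of the CT scan conforming tumour progression, the change of treatment due to unacceptable toxicity, death from any cause", or otherwise to last follow-up. Time to progression (TTP) in the same section counts objective progression only. In SAP 7.2.4, PFS runs "until the date of progression/death or change of treatment for unacceptable toxicity" and is otherwise censored at last follow-up. The protocol's abbreviation list ends DOR only at the CT scan showing progression.
- **Definition of CR.** SAP 5.1 requires "documented disappearance of all lesions in the investigator's opinion in at least 2 consecutive CT scans". SAP 5 has the looser "disappearance of all measurable lesions according to the investigator's criterion in at least 2 consecutive CT scans". The protocol has the same split between its objectives and its abbreviation list.

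**The concern.** The objective and the recorded variable treat stabilisation as a way for CR to end that is distinct from progression. The analysis has no place for it. A site might see a small lesion return and then stay unchanged, enter stabilisation as the reason, and enter no progression date. Under the written rules that patient has no event on that date, and the time after CR ended is counted as remission.

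Median CR duration is a named secondary objective. SAP 7.2.4 also says that the time-to-event results, including the Cox model, will support recommendations on treatment strategy after CR. An upward bias in these estimates would make remissions look more durable than they were.

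**Working it through.** **Step 1. Compare the lists of ways CR can end.**

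| Source | Progression | Stabilisation | Toxicity | Death |
|---|---|---|---|---|
| Secondary objective (protocol 7.2; SAP 2.2, 5.1) | yes | yes | yes | yes |
| Reason variable (protocol variables table; SAP 5.4) | yes | yes | yes | no |
| DOR (SAP 5) | yes | no | yes | yes |
| TTP (SAP 5) | yes | no | no | no |
| PFS (SAP 7.2.4) | yes | no | yes | yes |
| DOR (protocol abbreviation list) | yes | no | no | no |

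Stabilisation is in the objective and the reason variable and in none of the analysed endpoints. PFS in SAP 7.2.4 is the operational form of the objective in SAP 5.1, and it drops this one component without comment. The post-treatment items in SAP 5 include dates for end of treatment, progression and death, but no date for loss of CR by any other route.

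**Step 2. Follow one patient under the written rules.** CR is recorded as ended by stabilisation at time T, with no progression date. There is no DOR, TTP or PFS event at T. The interval runs to a later qualifying event or to last follow-up. Either endpoint is at or after T, so the error has one direction.

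**Step 3. Illustrate the size.** The documents contain no figure to reproduce, so this step rests on assumptions.

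Inputs:
- True median from CR to its end, m: 27.6 months (Czech registry, PFS from CR) or 7.9 months (hospital series, TKI alone). Both are cited in protocol 6 and SAP 2.
- Share p of CR endings coded stabilisation with no progression date at that time: assumed 5%, 10% and 20%.
- Exponential times and independent censoring: assumed.

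*Case A: no later event, censored at last follow-up.* These patients never have an event, so the Kaplan-Meier curve estimates p + (1 − p)·2^(−t/m). Setting this to 0.5 gives

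median = m × log2[(1 − p)/(0.5 − p)].

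- p = 5%: log2(0.95/0.45) = 1.078, so 27.6 becomes 29.8 and 7.9 becomes 8.5.
- p = 10%: log2(0.90/0.40) = 1.170, so 27.6 becomes 32.3 and 7.9 becomes 9.2.
- p = 20%: log2(0.80/0.30) = 1.415, so 27.6 becomes 39.1 and 7.9 becomes 11.2.

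*Case B: progression recorded later, assumed median 12 months after T.* With λ = ln2/m and μ = ln2/12, solve

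(1 − p)·e^(−λt) + p·(μe^(−λt) − λe^(−μt))/(μ − λ) = 0.5.

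| p | m = 27.6, case A | m = 27.6, case B | m = 7.9, case A | m = 7.9, case B |
|---|---|---|---|---|
| 5% | 29.8 | 28.5 | 8.5 | 8.4 |
| 10% | 32.3 | 29.5 | 9.2 | 8.9 |
| 20% | 39.1 | 31.3 | 11.2 | 10.0 |

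A simulation with 200,000 patients and follow-up uniform on 0–120 months gives the same values to within 0.1 month.

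**Step 4. Compare with sampling error.** With 90 patients, a true median of 27.6 months and follow-up uniform on 9–138 months (assumed), 95% of simulated Kaplan-Meier medians fall between about 20 and 37 months with no miscoding. Most of the shifts above are smaller than that spread. They are systematic, however, and the confidence interval does not reflect them.

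**The case against.** The strongest reply is that the SAP collects a progression date separately, and nothing shows that choosing stabilisation as the reason would stop a site from entering one. If sites date every reappearance as progression, DOR and PFS are correct. The protocol's abbreviation list also asks for continuing CR to be indicated, defined by an unchanged last scan, and a patient with a returned lesion should not qualify. Both points stand as partial safeguards. They do not close the gap: no rule requires a reappearance to be dated as progression, neither document defines progression, and the continuing-CR flag is not used in the SAP's censoring rules.

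A reader might infer more than the documents support:

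- *That every such relapse is carried as remission.* This happens only when no progression date is entered.
- *That stabilisation cannot follow CR unless a lesion returns.* That is strict under the all-lesions definition. Under the measurable-lesions wording, non-measurable disease that persisted throughout could be called stable.
- *That a table of reasons for the end of CR will fail to match the event count.* No such table is planned. The reason table in SAP 7.2.3 concerns stopping treatment and does not list stabilisation.
- *That a lesion-free patient described as stable would have CR cut short.* Stabilisation is not an analysed event, so no interval is shortened.
- *That leaving death off the reason list loses deaths.* Deaths are dated separately and counted in DOR and PFS, so this is a matter of consistency only.

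It is also fair to say that this is a registry without a hypothesis and that the endpoints affected are secondary.

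**Conclusion.** The inconsistency is real. The objective and the recorded variable let CR end by stabilisation, the analysed endpoints do not, and the term is undefined. Where stabilisation is recorded without a progression date, the written rules count time after the end of CR as remission, which conflicts with the SAP's own reading of DOR as disease-free survival time.

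The bias is upward and its size cannot be known from the documents. For an assumed 5–20% of endings coded this way, a true median of 27.6 months is overstated by about 1 to 4 months (28.5–31.3) if progression is recorded later, and by about 2 to 11 months (29.8–39.1) if patients are censored at last follow-up. These figures rest on the assumed share, exponential times and, in the first case, an assumed 12-month median to recorded progression. If sites always enter a progression date for a reappearing lesion, the bias is zero. The point should be settled before analysis, but it does not threaten the registry as a whole.

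**What to change.** 1. Make the objective (protocol 3 and 7.2; SAP 2.2 and 5.1), the reason list and the DOR, TTP and PFS event lists agree. Either remove stabilisation throughout, or define it and count it as a dated end of CR in DOR and PFS.
2. Add a coding rule to the SAP. A stabilisation entry with a visible reappearing or new lesion ends CR on the date of that scan. An entry without one is continuing CR.
3. Query any stabilisation entries already made, asking for the scan date and whether a lesion was visible. SAP 5.4 describes the covariates as already collected, so this does not depend on changing the CRF.
4. Reconcile the all-lesions and measurable-lesions definitions of CR, because the meaning of stabilisation depends on which applies.
5. Add death to the reason list for consistency with DOR and PFS.

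The cost is wording changes in the two documents, a few data queries and possibly a slightly shorter reported median.
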